Attention deficit/hyperactivity disorder (ADHD) is one of the most common neurodevelopmental disorders frequently diagnosed in school-aged children. It is characterised by pervasive symptoms of inattention, hyperactivity, and impulsivity. There are three main types of ADHD: inattentive type, hyperactive-impulsive type, and combination type. ADHD impacts the children's emotions, behaviours and ability in learning. The hyperactivity and inattention levels of children with ADHD are noticeably higher than expected, causing distress or problems at home, at school and with peers. The global prevalence rate of ADHD is about 5% to 7%. According to the data from the Family Council in Hong Kong, there are 14,580 students with ADHD in Hong Kong, which is the second-highest number among the nine types of special education needs (SEN). Children with ADHD's executive functions can be delayed by up to 32% compared with peers. Such delay may cause difficulty in self-control, managing emotion, paying attention and holding information in working memory, and likely to talk excessively and interrupt others. Hence, children with ADHD have challenges in understanding social cues and behaviour problems while entering a social setting. For example, they are difficult to comprehend some nonverbal expressions (body language, eye contact and facial expressions) and spoken communication (pitch, speed, tone, and volume), leading to difficulty in listening to others, sharing scattered thoughts and rapid speaking. The social skill deficit causes becoming hard to build friendships and integrate into society. ADHD has been associated with a wide range of detrimental impacts on affected subjects and with a severe financial burden to families and society. Several studies reported that the economic burden of raising a child with ADHD was five to six times more than the counterpart and parents of those with ADHD tended to be fired and have low work efficiency. Therefore, adequate and appropriate treatments should be provided to alleviate their behaviours and costly dysfunctional outcomes in the community. The commonly used social skill training in children with ADHD are tradidactic instructions, modelling, role-play activities and behaviour rehearsal; however, these methods are limited to time and space and short of real-life scenarios.

Virtual reality (VR) has emerged in plenty of domains as a promising tool for therapy and rehabilitation. Numerous studies adopted VR in improving cognitive behaviours in children

with ADHD; however, the focuses of these studies were cognitive functioning of daily living context, attentional performance and impulsivity. None of these studies utilised VR to improve social interaction competence and appropriateness in children with ADHD.

Furthermore, VR provides controllable immersive environments to engage children, sustain their attention and allow them to effectively gain skills in a safer environment. VR systems generally consist of a head-mounted display and screen so that the therapy can be conducted in a relatively low spatial limitation. Although no study has investigated VR social interaction skills in children with ADHD, evidence has proposed the use of VR social skill training in children with Autistic Spectrum Disorder (ASD). Most of the studies regarding children with ASD also used some real-life scenarios, for example, classrooms, transportation and supermarket, in their social skills training program. The differences in social skills between ADHD and ASD are that children with ADHD are easy to be distracted, avoid or dislike concentrating on one thing and are more likely to interrupt others' speaking; those with ASD are less aware of others around them, overly attached to one object that they like and hard to give meaning to their speech. Due to these discrepancies, the design of social VR intervention in this study will be put in more instantaneous events, objects and avatars in each scenario to improve the distraction problems of children with ADHD. In addition, social VR, which allows more than one user to appear as avatars in a lifelike environment and connect with other users in real-time, will be adopted in this study instead of VR to enhance engagement and interaction among children with ADHD.

Considering the prevalence and advantages of social VR, we plan to develop a social VR training program that contains three real-life scenarios and compare the effects of social VR training and traditional social skills training on social interaction skills, inhibitions, emotional control, behavioural and emotional difficulties and conduct disorders for children with ADHD in Hong Kong using receiving no training as a control.

Cultivating sufficient and appropriate social interaction skills for children with ADHD is a vital step to assist them in integrating into the community. The real-life scenarios created by VR offer a more effective alternative to therapeutic strategies for children with ADHD. However, no previous study adopted social VR to assess social interaction competence and appropriateness in children with ADHD and no randomised controlled trial (RCT) compared the effectiveness of social VR training and traditional social skills training on enhancing the social interaction skills in children with ADHD. The traditional social skills training for

children with ADHD lacked the provision of real-life scenarios and was limited by time and space. Social VR allowing real-time connection and interaction between patients and the virtual instructor was absent in previous studies. To fill these research gaps, we proposed to conduct a three-arm RCT to answer the research question of whether social VR training has higher effectiveness than traditional social skills training in enhancing the social interaction skills of children with ADHD in Hong Kong. The findings of this study are expected to unveil the clinical impacts and compliance and acceptability of social VR training for enhancing social interaction skills among children with ADHD.

To fill these research gaps, we proposed to conduct a three-arm RCT to answer the research question of whether social VR training has higher effectiveness than traditional social skills training in enhancing the social interaction skills of children with ADHD in Hong Kong. The findings of this study are expected to unveil the clinical impacts and compliance and acceptability of social VR training for enhancing social interaction skills among children with ADHD.

Aims and hypotheses

The study targets children with diagnosed ADHD and aims to (1) develop a social virtual reality-based intervention, (2) investigate its effects on improving the social skills and executive functioning of inhibitions, emotional control and attention of the children compared to traditional social skills training and (3) evaluate the subjects acceptability and compliance with social VR training for enhancing social interaction skills. It is hypothesised that the social interaction skills of the participants in the social VR training group are likely to perform better than those in the traditional social skills training group. Participants in the waitlist control group will receive no change in social interaction skills compared with the two intervention groups.

Methods/ Design

The study will be a three-arm randomised controlled trial comparing the effects of a social VR-based intervention with traditional social skills training on social skills and executive functioning of children with ADHD. Participants in the social VR intervention group and traditional social skill training group will receive 12 training sessions for 3 weeks (4 sessions per week), and participants in the waitlist control group will be asked to retain their usual lifestyles for 3 weeks. The overall design of the study is illustrated in Figure 1. Ethical

approval for the study has been obtained by the Human Subjects Ethics Application Review Committee of The Hong Kong Polytechnic University.

[figure not shown]

Figure 1. Study design

Participants

Individuals who meet the inclusion criteria will be recruited. The criteria are as follows: 1) aged between 6 and 12 years; 2) ethnic Chinese; 3) residing in Hong Kong; 4) having received a diagnosis of ADHD by Child Assessment Service in Hong Kong or via private practice; 5) stable on pharmacological and/or psychological treatment for ADHD 8 weeks before baseline (determined by health care professionals on the basis of medication data and behavioural observation); 6) no initiation or change of pharmacological treatment for ADHD during the intervention period; 7) ability to read Chinese, and speak and listen to Cantonese by the child and by at least one of their parents or legal guardian; 8) willing to provide informed consent by both participants and one of their parents or legal guardian.

Exclusion criteria are as follows: 1) comorbid autism; 2) mental retardation; 3) an estimated

IQ lower than 85 (using the Wechsler Intelligence Scale for Children – Fourth Edition (Hong Kong) (WISC-IV(HK))); 4) autism spectrum disorder (previously diagnosed by health care professionals), 5) comorbid acute psychiatric disorder (previously diagnosed by health care professionals); and 6) with a severe physical disability (e.g., blindness, deafness) or learning disability (e.g., dyslexia).

Sample size

The guidelines of Whitehead et al. (2016) suggested that recommended that at least 16 subjects per group for medium effect size in pilot RCT and 15% attrition over time can be expected. A total of 90 participants will be recruited which fulfils the minimum number suggested by Whitehead et al. (2016). 30 participants in the social VR group, 30 in the traditional social skills group and 30 in the waitlist control group. This sample size is comparable to those used in the published pilot study on children with ADHD. For instance, van der Oord et al. (2014) recruited 40 participants (20 in the control group and 20 in the interventional group) to examine the efficacy of computerized executive functioning remediation training with game elements in children with ADHD.

Procedure

Recruitment

Participants will be recruited from six primary schools and community centres. Interested participants or parents who provide written informed consent will be further evaluated for inclusion and exclusion criteria by a trained research assistant. Participants who meet the inclusion criteria in the study will be invited to perform an IQ test at the university at baseline.

Randomisation

Eligible participants will be randomized to the social VR (Social VR) group, traditional social skills training group or waitlist control group. A computer-generator randomiser will be used to generate the random allocation list. The randomisation will be undertaken by another research assistant not directly involved in the study. A number generated by the computer will be assigned to each eligible subject who will be randomly allocated to the three different groups by using the number. The participants and their parents or legal guardians will be blind to the assignment process. Parents or legal guardians will receive an email and a telephone call with notification to Group 1, Group 2 or Group 3.

Social VR Intervention

Social VR intervention is developed to enhance the social interaction skills of children. The participants will wear a head-mounted display (HMD) for the Social VR intervention. Each session of the Social VR intervention lasts for a maximum of 20 minutes to ensure the participants focus on the intervention and prevent causing any physical effect. The duration will be adjusted depending on the emotion of the participants during the intervention. The Social VR intervention will mainly help the participant to enhance their social interaction skills and executive function. The intervention contains three real-life virtual scenarios, including (1) classroom and playground, (2) MTR station and compartment, and (3) street and building. One scenario will be adopted in each session. The sequences of the scenarios used in each session will be the same for all participants. During the Social VR intervention, one RA will also appear as one avatar in the scenario to guide the participants to complete a series of tasks. Each intervention session will be conducted in a classroom independently for each participant.

Traditional social skills training

An experienced SEN teacher will teach the participants social interaction skills through tradidactic instructions and role-play activities. Four modules will be covered in the 3-week training: (1) how to introduce yourself and basic social skills; (2) how to listen to others; (3) how to share with others; (4) learn to know how people feel and how to empathise. These modules have been applied in many studies. The content of this training will be as similar as possible to the Social VR training. The training lasts 20 minutes which depends on the emotion of the participants. Each training session will be conducted in a classroom independently for each participant.

Waitlist control group

The participants in this group will receive no training and they can participate in the social VR training after the intervention period. To ensure consistency of the experiment, the participants are not allowed to initiate or change their pharmacological treatment during the 3-week intervention period.

Measures

Questionnaires

The parents or legal guardians of the participants will complete a structured questionnaire at the baseline and after the last session. Demographic information, including age, gender, Medication, ADHD symptoms and game experience will be recorded at the baseline. The questionnaires include questions about social skills and executive functioning. The satisfaction of the participants and their parents or legal guardians towards the training program will be assessed at week 3. The VR sickness of the participant will be evaluated after each session. The assessor will be blind to the treatment condition. The questionnaires will include the following scales:

Primary outcome measure

1. Process evaluation

The process evaluation of the training will be assessed by investigating: (i) training acceptability as measured by the participants' attendance and compliance; (ii) recruitment rate; (iii) participant completion.

(i) Assessment of training acceptability and compliance

The attendance of the participants during the trainings will be recorded. To verify the validity of the findings, training non-adherence of the participants will be terminated which will be stated in the consent form. The absence of any training session will be considered as non-adherence. The participants will be asked about their willingness of partaking in this kind of training by one 7-point Likert scale question which is used to reflect the acceptability to the intervention. The retention rate should be at least 85% according to the feasibility RCT.

The compliance with the training program will be evaluated by the communication log which the parents record their children's daily activity and emotion in the 3-week intervention period. The participants' parents will be reminded to attend the training through telephone in the first four training sessions and WhatsApp or WeChat in the fifth and eighth training sessions. No reminder follow-up will be made in the remaining four sessions. These data will be used to evaluate their compliance.

(ii) Recruitment rate

The recruitment rate is at least 48.5% of all referrals according to the feasibility study.

(iii) Participant completion

Participants attending at least nine (i.e., 75%) of the 12 sessions are considered to have completed the program.

Secondary outcome measure

1. Social Skills Rating Scale (SSRS-P)

The social skills of the children will be assessed by Chinese-translated SSRS-P which will be scored by the participants' parents before the first session and after the last session. This scale consists of 3 subscales, including self-control, assertiveness and initiative and cooperation, with a total of 31 items. A 3-point Likert scale (never, sometimes, often) is used to score. The SSRS-P is a validated instrument that has been commonly adopted in clinical trials of psychiatric and neurological disorders.

2. Child psychologist's assessment

One child psychiatrist will score the performance of the participants in the 5-minute tasks to obtain an objective evaluation. Broken blinding is unavoidable in child psychiatrist's assessment. To minimise unblinding bias during the assessment, each participant will be identified by a case number.

3. Behaviour Rating Inventory of Executive Function (BRIEF)

Chinese-translated BRIEF used to assess the executive functioning of children which will be scored by the participants' parents before the first session and after the last session. The subscales of inhibitions (16-item) and emotional control (10-item) will be adopted in this study. A 3-point Likert scale (never, sometimes, often) is used to score.

4. Satisfaction

Satisfaction is measured by a 7-point Likert scale, 'What grade would you give to this training program?'. Both participants and parents/ guardians have to answer.

5. Simulator Sickness Questionnaire (SSQ)

The SSQ measures motion sickness or physical discomfort of participants in VR environment. Nine items will be measured, including discomfort, fatigue, headache, eyestrain, sweating, nausea, difficulty concentrating, blurred vision and dizziness, with yes or no questions for each item.

6. Assessment of safety

a) Adverse events

RA1 will ask participants' parents/ guardians, using open-ended questions, whether the participants experienced any adverse events during training. The severity and relationship of the adverse event to the intervention will be documented and investigated.

b) Reasons for withdrawal

When a subject withdraws before completing the study, the reasons for withdrawal will be recorded.

Statistical analysis plan

All statistical analyses will be performed in SPSS version 26.0 software (IBM Corp, Armonk, NY, USA) and are two-sided with a level of significance of < 0.05 . Demographic information of the participants will be summarised with frequency and percentage for categorical variables. The continuous variables will be summarised by mean and standard deviation. The change between baseline and week 3 within each arm will be tested using t-tests. To examine the between-group difference in terms of measure outcomes from baseline to week 3, repeated analyses of covariance (ANCOVA) with adjustment of baseline characteristics will be conducted. To evaluate the improvement during the intervention period among the three groups, f-tests will be performed on primary and secondary outcome measures at the beginning of the first session and at the end of the last session. An intention-to-treat analysis will be performed. This analysis is regarded as the most appropriate approach to analyse RCT data by the highest-quality journals, which have utilised the CONSORT standard.

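### The protocol expects physical effects from the headset, but no eligibility item asks about a child's known susceptibility to them before randomisation

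*Combined protocol and SAP*

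**What the plan says.** **Who is eligible.** The Participants section lists 8 inclusion criteria: age, ethnicity, residence, ADHD diagnosis, stable prior treatment, no treatment change during the intervention, language and consent. The age criterion is "aged between 6 and 12 years". The 6 exclusions are autism (listed twice, in slightly different words), mental retardation, low IQ, "comorbid acute psychiatric disorder (previously diagnosed by health care professionals"), and children "with a severe physical disability (e.g., blindness, deafness) or learning disability (e.g., dyslexia").

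**What they are exposed to.** Under Social VR Intervention: "The participants will wear a head-mounted display (HMD) for the Social VR intervention". Under Methods/Design, both training groups "will receive 12 training sessions for 3 weeks (4 sessions per week"). Waitlist children may take up the VR training after the intervention period (Waitlist control group).

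**What effects are expected.** Each VR session "lasts for a maximum of 20 minutes to ensure the participants focus on the intervention and prevent causing any physical effect". The Questionnaires section has VR sickness assessed after each session. The Simulator Sickness Questionnaire (SSQ, secondary outcome 5) asks yes/no about "discomfort, fatigue, headache, eyestrain, sweating, nausea, difficulty concentrating, blurred vision and dizziness".

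**What happens if a child is unwell.** The rule for changing session length names mood only: "The duration will be adjusted depending on the emotion of the participants during the intervention". Parents are asked open-ended questions about adverse events, whose severity and relationship to the intervention are documented and investigated. Reasons for withdrawal are recorded (secondary outcome 6).

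**The concern.** The plan names a hazard, limits exposure because of it and measures it twelve times, but does not ask beforehand whether a child is known to be vulnerable to it. The research assistant who checks eligibility has no item on the subject. The listed baseline variables include game experience but no history of motion sickness or similar problems.

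What is at stake is mainly safety. These are young children receiving repeated exposures, and the information could be obtained from a parent in minutes before allocation. A second matter is interpretation. If a child with a known problem stops using the headset, the trial learns something that could have been known at screening, and the documents give no rule for showing that loss separately from other non-adherence.

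**Working it through.** The point rests on an omission, so the main check is to set the criteria against the expected effects. The arithmetic only sizes the exposure and one related conflict.

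**1. Criteria against expected effects.**

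| Criteria (Participants section) | Bears on headset susceptibility? |
|---|---|
| Inclusion 1-3, 7, 8: age, ethnicity, residence, language, consent | No |
| Inclusion 4-6: diagnosis, stable treatment, no treatment change | No; these concern ADHD and its treatment |
| Exclusions 1, 4: autism | No |
| Exclusions 2, 3: mental retardation, low IQ | No |
| Exclusion 5: acute psychiatric comorbidity | No |
| Exclusion 6: severe physical or learning disability | Partly: a severe visual impairment might fall under it; a history of becoming unwell with motion or screens would not obviously do so |

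No criterion addresses the nine SSQ symptoms or a tendency to develop them.

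**2. Timing of the existing safeguards.**

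| Safeguard | When it acts |
|---|---|
| 20-minute maximum | During exposure |
| Adjustment of session length | During exposure, for emotion; physical symptoms are not named |
| SSQ | After each session; no action is tied to a result |
| Adverse-event questions | About events during training |
| Reasons for withdrawal | When the child leaves |

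None acts before allocation.

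**3. Scale of exposure.** Inputs: 3 weeks and 4 sessions per week (Methods/Design), at most 20 minutes per session (Social VR Intervention), 30 children per group and 90 in all (Sample size).

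- Sessions per child: 3 × 4 = 12, as the plan states.
- Longest headset time per child: 12 × 20 = 240 minutes over 3 weeks.
- Children who could wear the headset: 30 in the VR arm plus up to 30 from the waitlist, so up to 60 of 90. The documents do not say how long the later waitlist programme lasts.

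The number of these children with a relevant known history cannot be computed; the documents give no rate.

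**4. What one sickness absence costs.** The Primary outcome measure section contains two rules. One treats absence from any session as non-adherence, which leads to termination. The other counts attendance at nine or more sessions as completion: 9/12 = 75%, as stated, which tolerates 12 − 9 = 3 missed sessions. Take a child who misses one session through sickness.

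- If the child continues and attends the rest, attendance is 11/12 = 91.7% and the child completes.
- If the child is terminated at a first absence in session k, attendance is k − 1. Completion needs k − 1 ≥ 9, so k ≥ 10. A first absence in sessions 1 to 9 means non-completion; in sessions 10 to 12 the child still counts as a completer.

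The same event therefore gives opposite results depending on which rule governs, and neither makes an exception for sickness.

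**The case against.** **Intolerance is a result, not contamination.** Aim 3 is to evaluate acceptability of and compliance with social VR, and the primary outcome covers attendance, compliance and completion. A child who cannot tolerate the headset is informative about exactly that. This stands: it is a reason not to treat headset-related losses as bias. It does not argue against asking about a history already known to the parent.

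**A reader might infer that the gap will push the VR arm below the 85% retention target.** The documents do not support this, for four reasons.

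- They give no intolerance rate.
- They do not say whether 85% applies to each arm or overall. Per arm it needs 26 of 30 (0.85 × 30 = 25.5); overall, 77 of 90 (0.85 × 90 = 76.5). At assumed VR dropout of 10%, 15% and 20%, the binomial probability of reaching the target is 0.82, 0.52 and 0.26 per arm, but 0.94, 0.84 and 0.69 overall with 10% dropout assumed in the other arms. The answer turns on assumptions the plan does not settle.
- Only intolerance with a known history could be screened out, and that share is unknown.
- A child who attends despite symptoms still counts as retained and complete.

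**Exclusion 6 may already cover severe cases.** Blindness and deafness are only examples, so a severe visual or balance disorder might be excluded. It is therefore too strong to say that every vulnerable child passes. But the wording leaves this to the assistant's judgement and does not obviously reach a non-disabling susceptibility.

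**Other safeguards exist.** Sessions are individual and guided by a research assistant, adverse events are investigated, ethics approval was obtained, and withdrawal reasons are recorded. The consent pages are not in the text reviewed and may contain health questions or warnings. All of this is fair. The safeguards visible in the documents still act after allocation, and a consent-page warning would not be an eligibility rule.

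**Conclusion.** The point holds as a safety gap in eligibility. The protocol expects physical effects of the headset, has no criterion on known susceptibility beyond an imprecise disability exclusion, and relies on measures that act only after exposure begins. It is a change the sponsor should make, not a fatal flaw.

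The exposure is known: up to 12 sessions and 240 minutes per child in the VR arm, with up to 60 children potentially wearing the headset. The number of susceptible children is not known. The conclusion needs no assumed rate. It assumes only that the criteria list in the protocol is complete and that no separate screening is described in the removed consent pages.

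The conclusion does not extend to bias in the retention or completion results. Intolerance among eligible children is a legitimate finding of this trial.

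**What to change.** 1. **Add one eligibility item**, asked of parents by the research assistant at the existing screening step, before randomisation and identically for all three arms. It should cover known susceptibility to the effects the protocol itself lists. Its clinical content is for the investigator to set; none is proposed here.
2. **Repeat the item** before any waitlist child takes up VR.
3. **Report headset-related withdrawals separately**, using the withdrawal reasons already recorded, while still counting them in the acceptability and retention results.
4. **Reconcile the two attendance rules** in the Primary outcome measure section (termination for any absence; completion at nine of 12 sessions), and state what a sickness absence counts as. Which rule applies is for the sponsor to decide. State also whether the 85% retention target is per arm or overall.

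**Cost.** One criterion, a short parent question set at a contact that already takes place, and one extra line in the withdrawal table. A few children may be excluded, and the tolerability results will then apply to screened children only, which the report should say. Applying the item before randomisation and to all arms keeps the groups comparable.

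### VR sickness is asked after each session with no per-session starting value and no clear non-VR comparator, so its rates may mix background ADHD symptoms with VR effects

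*Combined protocol and SAP*

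**What the plan says.** Under Measures, Questionnaires: "The VR sickness of the participant will be evaluated after each session". Secondary outcome 5 describes the instrument: "The SSQ measures motion sickness or physical discomfort of participants in VR environment". Its content is: "Nine items will be measured, including discomfort, fatigue, headache, eyestrain, sweating, nausea, difficulty concentrating, blurred vision and dizziness", answered "with yes or no questions for each item". There is no severity grade, no option for new or worse since the session began, and no scoring, attribution or analysis rule.

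The introductory account of ADHD says: "It is characterised by pervasive symptoms of inattention, hyperactivity, and impulsivity". Of delayed executive function it adds: "Such delay may cause difficulty in self-control, managing emotion, paying attention and holding information in working memory".

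Three other places bear on the point:

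- The Statistical analysis plan has one general sentence that puts all primary and secondary outcomes at the start of session one and the close of the final session, compared across three groups. The SSQ is listed as a secondary outcome.
- For the SSRS-P and BRIEF, the outcome descriptions themselves name a pre-training and a post-training assessment. The SSQ description does not.
- Adverse events are collected separately through open questions to parents or guardians, and their relationship to the intervention is documented.

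**The concern.** The SSQ is the only VR-specific tolerability measure in the trial. A symptom reported after a session can be attributed to the session only if one knows whether it was there beforehand, or how often children report it after a comparable session without VR. The plan clearly provides neither. At least one of the nine items asks about something that the protocol itself treats as characteristic of the children enrolled.

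The error could go either way. Background inattention could be read as poor tolerability of the headset, or a real VR effect could be dismissed as ordinary ADHD. In a pilot of a new intervention whose main question is acceptability and completion, tolerability is among the results that readers will want to rely on.

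**Working it through.** **Inputs from the documents.** Four sessions a week for three weeks gives 4 × 3 = 12 sessions. Ninety children in three equal arms gives 90 / 3 = 30 per arm. Expected attrition is 15%. The documents give no SSQ rate, threshold or power, so there is no figure of the plan's own to reproduce.

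**Input that is assumed.** The chance *p* that a child answers yes to difficulty concentrating after a session for reasons unrelated to VR. I take 10%, 20% and 30% as illustrations.

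**Step 1: timing.** The Questionnaires section gives a post-session value, 12 times per child. The general sentence in the Statistical analysis plan, read literally, gives one value before any exposure and one at the end, in three groups. These are different schedules. Even the literal reading supplies no value before sessions 2 to 12. It also fits a VR-sickness scale poorly, since waitlist children receive no training in that period.

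**Step 2: expected positive forms.** The VR arm yields 30 × 12 = 360 forms with full attendance. If 15% were lost from the start, it yields 0.85 × 360 = 306. The expected number of background positives is forms × *p*, whatever the correlation within a child.

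**Step 3: children ever positive in 12 sessions.** This depends heavily on correlation within a child:

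- Full correlation: *p*.
- Independent sessions: 1 − (1 − *p*)^12.
- Assumed intermediate case, beta-binomial with correlation 0.5: a + b = 1/0.5 − 1 = 1, so a = *p* and b = 1 − *p*. The chance of never being positive is the product over i = 0 to 11 of (1 − *p* + i)/(1 + i).

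| Assumed *p* | Positive of 360 | Positive of 306 | Ever, full correlation | Ever, correlation 0.5 | Ever, independent |
|---|---|---|---|---|---|
| 10% | 36 | 31 | 10% | 27% | 72% |
| 20% | 72 | 61 | 20% | 48% | 93% |
| 30% | 108 | 92 | 30% | 64% | 99% |

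All of these arise with no VR effect.

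**Step 4: what a traditional-arm comparator could show.** I compare per-child proportions, 30 against 30, two-sided 5%, normal approximation with pooled variance under the null. For 10% against 40%, the pooled rate is 25%. The null standard error is √(2 × 0.25 × 0.75 / 30) = 0.112, and the alternative standard error is √((0.09 + 0.24)/30) = 0.105. Then z = (0.30 − 1.96 × 0.112)/0.105 ≈ 0.77, so power is 78%. The same calculation gives 49% for 10% against 30%, 79% for 30% against 65%, and 84% for 50% against 85%. Only differences of roughly 30 to 35 points would be detected reliably, so the comparison is an estimate and not a powered test.

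**The case against.** A reader might infer that ADHD features will be counted as VR side effects. The documents do not go that far. No score, cut-off or attribution rule is given, and reporting by item would keep difficulty concentrating apart from nausea or dizziness. The text supports only that they may be.

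A reader might also state flatly that the SSQ is given only after VR sessions and that no earlier or comparator value exists. VR-only collection is the natural reading of the wording, but no arm is named, and the protocol uses 'session' for both training arms. The general sentence in the Statistical analysis plan, taken literally, implies one pre-exposure value and a three-group comparison. That does not supply per-session values, but it means the claim has to be put as a conflict between sections.

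A third tempting step is to quote 72% to 99% of children ever positive as the size. Those figures assume independent sessions, while a persistent trait implies strong correlation within a child. Similarly, a 2% background on each of nine items gives 1 − 0.98^108 = 89% of children with at least one positive, but only by treating 108 answers as independent draws. The documents tie just one item to ADHD. They do not say that fatigue, headache or discomfort are common on any day.

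Finally, other data bear on attribution: adverse events with a documented relationship, the parents' daily log, and the baseline record ("Demographic information, including age, gender, Medication, ADHD symptoms and game experience will be recorded at the baseline"). These help with context, but none uses the SSQ items session by session, so none makes a post-session answer interpretable. The objection stands on certainty and size. It does not remove the gap.

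**Conclusion.** The concern holds in a limited form. As written, and on the natural reading, post-session SSQ rates cannot be attributed to VR, because there is no value before each session and no clear non-VR comparator. The overlap with ADHD is documented for one item of nine.

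The firmest measure of size is the expected count: about 36, 72 or 108 of 360 forms at assumed background rates of 10%, 20% or 30% with full attendance. The per-child figure is uncertain across the whole range from full correlation to independence. Since the documents give no background rate, all of this is illustration.

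This affects one secondary tolerability measure. The primary process outcomes and the sample size are untouched. The change is worth making because it is cheap and cannot be recovered after data collection.

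**What to change.** 1. Ask the same nine items immediately before and immediately after each VR session, and after each traditional session.
2. State which arms complete the SSQ and when. Amend the general sentence in the Statistical analysis plan so that it either excludes the SSQ or says how it applies.
3. Report by item, per session and per child, the symptoms that are new (no before, yes after) in the VR arm.
4. Report the post-session VR-minus-traditional difference with a confidence interval that treats the child as the unit, labelled as an estimate.

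The comparator should be part of the change. Concentration fluctuates, so a before/after count alone would still pick up ordinary variation. Because the items are yes/no, it would also miss a symptom that was present and got worse.

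The cost is about one extra minute per session and no extra visits. A research assistant already takes part in the VR sessions. In the traditional arm, the teacher or an assistant would hand over the form. The drawback is that questions beforehand may prime children aged 6 to 12. If only the VR arm is asked beforehand, priming could inflate the between-arm difference. Asking beforehand in both arms would remove that imbalance for about the same small cost.
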